10.5 Safety Analysis

CCI

A

similar summary will also be presented by severity. A graph will be generated to illustrate the incidence over time. Data from the Perlane-L group will be pooled with the no-treatment group.

All AEs will be coded according to MedDRA.

All AEs will be summarised by system organ class (SOC), preferred term (PT) and treatment. Since the no-treatment control group will receive treatment at the month 6 visit, only AEs occurring up until that time point will be included in this presentation, for both groups. Furthermore, all AEs will also be summarised by SOC and PT using the Perlane-L group for the whole study period, and also using the no-treatment group for the study period following their treatment at Month 6.

Related AEs will be summarised by SOC, PT and intensity. In addition, for related AEs the number of days to onset and the duration of event will be summarised by SOC and PT using mean, SD, min, max and median. Action taken for related AEs will also be summarised. Data from the Perlane-L group will be pooled with the no-treatment group.

Serious AEs will be listed.

Non related AEs will be summarised by SOC, PT, and intensity. This will be done as described for all AEs, i.e. based on the following subsets of data: first 6 months following treatment by treatment, the Perlane-L group for the whole study, and the no-treatment group for the period following their treatment.

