3.4.2 Adverse events

All AEs will be coded according to MedDRA. All AE summaries defined below will be presented by treatment (no treatment at baseline vs. all treated subjects (at baseline and Month 6)).

The number of subjects with AEs related to study product or injection procedure as well as the number of events will be summarized by SOC and preferred term (PT). In addition, AEs related to study product or injection procedure will be summarized by SOC, PT and intensity. The number of days to onset and the duration of related AEs will be summarized by SOC and PT using mean, SD, min, max and median.

Serious AEs and device deficiencies will be listed, if applicable.

Non related AEs will be summarized by SOC, PT, and intensity.

CCI

[figure not shown]

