3.5 Interim Analysis

Not applicable.

4 Determination of Sample Size

CCI

Effective

Effective date: 2017-04-21 09:20

 GALDERMA	<small>Title</small> Statistical Analysis Plan 43CH1507	<small>Doc id</small> MA-32268
--	---	--

CCI

5 Changes in the Analysis Planned in the Protocol

CCI

Cohorts used for analysis of adverse events will be defined differently, as follows.

Text in CSP:

“Since the no-treatment control group will receive treatment at the month 6 visit, only AEs occurring up until that time point will be included in this presentation, for both groups. Furthermore, all AEs will also be summarised by SOC and PT using the Perlane-L group for the whole study period, and also using the no-treatment group for the study period following their treatment at Month 6.”

Revised text in SAP:

“All AE summaries defined below will be presented by treatment (no treatment at baseline vs. all treated subjects).”

Version: 1.0

6 Reference List

 GALDERMA	Title Statistical Analysis Plan 43CH1507	Doc id MA-32268
---	--	----------------------------------

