TEAEs unrelated to product and/or injection procedure	xx	xx.x	xx	xx	xx.x	xx
of which were serious	xx	xx.x	xx	xx	xx.x	xx
Subjects with no AE reported	xx	xx.x	-	xx	xx.x	-

Note: Treatment with Perlane-Lido columns include data from subjects in the Perlane-Lido group after their initial treatment at baseline, as well as data from subjects in the Control group after their initial treatment at Month 6.

% = $100 * n/N$

 GALDERMA	Title Statistical Analysis Plan 43CH1507	Doc id MA-32268
---	--	----------------------------------

Table A 35. Related TEAEs by MedDRA System Organ Class, Preferred Term, and intensity (Safety)

Primary System Organ Class Preferred Term	Intensity	No treatment at baseline N=xx		Treatment with Perlane-Lido N=xx	
		Events	Subjects	Events	Subjects
Any related AE	Total	Xx	Xx (xx.x)	Xx	Xx (xx.x)
	Mild	Xx	Xx (xx.x)	Xx	Xx (xx.x)
	Moderate	Xx	Xx (xx.x)	Xx	Xx (xx.x)
	Severe	xx	Xx (xx.x)	xx	Xx (xx.x)
SOC1	Total	Xx	Xx (xx.x)	Xx	Xx (xx.x)
	Mild	Xx	Xx (xx.x)	Xx	Xx (xx.x)
	Moderate				
	Severe				
PT11	Total				
	Mild				
	Moderate				
	Severe				
PT12	Total				
	Mild				
	Moderate				
	Severe				
SOC2	Total				
	Mild				
	Moderate				
	Severe				
PT21	Total				

Note: Treatment with Perlane-Lido columns include data from subjects in the Perlane-Lido group after their initial treatment at baseline, as well as data from subjects in the Control group after their initial treatment at Month 6.

% = $100 * n/N$

 GALDERMA	Title Statistical Analysis Plan 43CH1507	Doc id MA-32268
---	---	----------------------------------

Table A 36. Duration (days) of related TEAEs by MedDRA System Organ Class and Preferred Term (Safety)

	No treatment at baseline N=xx							Treatment with Perlane-Lido N=xx						
	Ongoing	n	Mean	SD	Min	Median	Max	Ongoing	n	Mean	SD	Min	Median	Max
General disorders and administration site conditions														
Injection site xxx														
Injection site xxx														
ALL														

Note: Treatment with Perlane-Lido columns include data from subjects in the Perlane-Lido group after their initial treatment at baseline, as well as data from subjects in the Control group after their initial treatment at Month 6.

% = 100*n/N

Table A 37. Time to onset (days) of related TEAEs, by MedDRA System Organ Class and Preferred Term (Safety)

	No treatment at baseline N=xx							Treatment with Perlane-Lido N=xx						
	n	Mean	SD	Min	Median	Max	n	Mean	SD	Min	Median	Max		
General disorders and administration site conditions														

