Injection site xxx														
Injection site xxx														
ALL														

Note: Treatment with Perlane-Lido columns include data from subjects in the Perlane-Lido group after their initial treatment at baseline, as well as data from subjects in the Control group after their initial treatment at Month 6.

% = 100*n/N

 GALDERMA	Title Statistical Analysis Plan 43CH1507	Doc id MA-32268
---	---	----------------------------------

Table A 38. Action taken due to related TEAEs by MedDRA System Organ Class and Preferred Term (Safety)

[figure not shown]
System Organ Class Preferred Term	Action Taken							
	No treatment at baseline N=xx				Treatment with Perlane-Lido N=xx			
	None	Medication treatment	Non-pharmacological treatment or other procedures/tests	Subject withdrawn	None	Medication treatment	Non-pharmacological treatment or other procedures/tests	Subject withdrawn
General disorders and administration site conditions								
Injection site xxx								
Injection site xxx								
SOC 2								
PT 1								
PT 2								
...								
All								

Table A 39. Unrelated TEAEs by MedDRA System Organ Class, Preferred Term and intensity (Safety)

As Table A 35

[figure not shown]
 GALDERMA	<small>Title</small> Statistical Analysis Plan 43CHI1507	<small>Doc id</small> MA-32268
---	---	--

CCI

 GALDERMA	<small>Title</small> Statistical Analysis Plan 43CH1507	<small>Doc id</small> MA-32268
---	--	--

CCI

 GALDERMA	<small>Title</small> Statistical Analysis Plan 43CH1507	<small>Doc id</small> MA-32268
---	--	-----------------------------------

CCI

[figure not shown]

Figure A 11. Proportion of subjects affected by a specific event (to any intensity level) after touch-up (Safety)

As Figure A 10

 GALDERMA	Title Statistical Analysis Plan 43CH1507	Doc id MA-32268
--	---	----------------------------------

2017-04-21 09:20

Effective date:

Effective

Version: 1.0

SIGNATURES PAGE

Date	Signed by
2017-04-20 15:12	PPD
Justification	Approved by Owner
2017-04-21 06:29	PPD
Justification	Approved by Technical Expert
2017-04-21 07:58	PPD
Justification	Approved by Project Manager
2017-04-21 08:38	PPD
Justification	Approved by Technical Expert
2017-04-21 09:20	PPD
Justification	Approved by Technical Expert

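### Unrelated adverse events are shown as crude percentages for about 6 untreated months (if that column stops at Month 6) against a longer pooled treated period

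*SAP*

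**What the plan says.** Protocol 10.5 planned a like-for-like comparison. For all adverse events by treatment, because controls are treated at Month 6, "only AEs occurring up until that time point will be included in this presentation, for both groups"; later periods were to be summarised separately. Non-related events were to follow the same scheme, "based on the following subsets of data: first 6 months following treatment by treatment, the Perlane-L group for the whole study", with the controls' post-treatment period as a third subset. Only some summaries, including those of related events, were pooled: "Data from the Perlane-L group will be pooled with the no-treatment group".

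SAP section 5 replaces this openly: "Cohorts used for analysis of adverse events will be defined differently, as follows". SAP 3.4.2 then applies two columns to every summary: "All AE summaries defined below will be presented by treatment (no treatment at baseline vs. all treated subjects (at baseline and Month 6". The notes to Tables A 34 and A 35 define the treated column as Perlane-Lido subjects after their baseline treatment "as well as data from subjects in the Control group after their initial treatment at Month 6".

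Unrelated events appear in two places: a row of Table A 34, "TEAEs unrelated to product and/or injection procedure", which has its own serious sub-row, and "Table A 39. Unrelated TEAEs by MedDRA System Organ Class, Preferred Term and intensity (Safety", laid out as Table A 35. The shells of Tables A 34 and A 35 give event counts and subjects, with the percentage defined as 100 × n/N. Table A 32, on exposure, covers injection volume, depth and method, not time at risk.

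**The concern.** The two columns do not cover the same length of observation. Perlane-Lido subjects contribute a year or more, crossed-over controls about half a year, and the untreated column about half a year if it is cut at Month 6. A control who accepts treatment can count in both columns.

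An event unrelated to product or procedure accumulates with calendar time. Its crude percentage will therefore be higher in the treated column even if treatment does nothing. A reader who sees two percentages side by side will tend to read the difference as a treatment contrast.

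The protocol's six-month summary would have supported that reading far better. Under the SAP no visible table does. What is at stake is the interpretation of unrelated events, and more weakly of the overall adverse-event rows. The primary endpoint is not affected.

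**Working it through.** **Inputs.** Group B is 148 subjects at 3:1, so 111 and 37 (Protocol synopsis). The final visit is 12 months after last treatment in the Treatment Group and 6 months after last treatment in controls (Protocol 4.7, Tables 1 and 2). An optional touch-up at 4 weeks (28/30.44 = 0.92 month) resets that clock. Controls are offered treatment at Month 6 (Protocol 4.1). Touch-up share, control uptake, dropout and background event rate are not given, so ranges are shown.

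**Check of the schedule.** Protocol 4.3 states about 14 months per subject. Screening of 21 days (0.69 month) + 0.92 + 12 = 13.6 months in the Treatment Group; 0.69 + 6 + 0.92 + 6 = 13.6 in controls. With the widest visit windows both are 14.2. The stated figure is reproduced.

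**Mean follow-up, no dropout.** Treated mean = [111 × (12 + a) + 37u × (6 + a)] / (111 + 37u), where a is 0 or 0.92 and u is control uptake.
- Full uptake: (111 × 12 + 37 × 6)/148 = 10.5 months; with touch-up for all, (111 × 12.92 + 37 × 6.92)/148 = 11.4.
- Half uptake: (111 × 12 + 18.5 × 6)/129.5 = 11.1 months; with touch-up, 12.1.
- Untreated: 6 months if cut at Month 6. If half decline and their later time stays in this column, (6 + 12)/2 = 9.0.

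At full uptake this is 37 × 6/12 = 18.5 untreated patient-years against 129.5-140.8 treated.

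**Effect on unrelated-event percentages.** Assume the same constant hazard in both columns and a six-month risk p. The risk over t months is 1 − (1 − p)^(t/6). At full uptake the treated column is 0.75 of the Perlane-Lido risk plus 0.25 of the crossed-over risk. For p = 20% without touch-up, 0.75 × 36% + 0.25 × 20% = 32.0%; with touch-up, 0.75 × 38.15% + 0.25 × 22.69% = 34.3%.

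| Assumed six-month risk | Untreated, cut at Month 6 | Treated, full uptake, no dropout |
|---|---|---|
| 10% | 10% | 16.75-18.1% |
| 20% | 20% | 32.0-34.3% |
| 40% | 40% | 58.0-61.2% |

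**Sensitivity at p = 20%.**
- Half uptake: treated (111 × 36% + 18.5 × 20%)/129.5 = 33.7%, or 35.9% with touch-up. Untreated is 20.0% if cut at Month 6, or (20% + 36%)/2 = 28.0% if decliners' later time counts as untreated.
- Exponential dropout of 10% a year: 19.5% against 30.7-32.8%. At 20% a year: 19.0% against 29.4-31.3%.

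**Any-AE and TEAE-total rows of Table A 34.** Suppose a share q of treated subjects has a related event, independently of unrelated ones. The treated figure is then 1 − (1 − q)(1 − unrelated risk). With q = 60% and p = 20%, it is 68.0% over six months and 72.8-73.7% pooled, an inflation of 4.8-5.7 points. At q = 30% the inflation is 8.4-10.0 points and at q = 80% it is 2.4-2.9. Injection reactions already count many treated subjects, so these rows move less.

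**Check of an equal window.** Six months is 182.6 days; less the one-week visit window it is 175 whole days. A Day 1-175 count gives 1 − 0.8^(175/182.6) = 19.3% in both groups when hazards are equal. A cut at the Month 6 visit would not be equal, because SAP 1.4.1 times that visit from last treatment in one arm and from randomisation in the other. With touch-up, 20% becomes 1 − 0.8^(6.92/6) = 22.7%.

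**The case against.** Several points on the other side stand.

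- **Declared and descriptive.** SAP section 5 announces the new cohorts, so a reader should not infer an undisclosed departure from the protocol. It does quote only the protocol's all-event text and not its separate sentence on non-related events. SAP 3.4 makes safety descriptive, and no between-group adverse-event test is visible.
- **Redaction.** Text is blacked out directly after the sentence on non-related events in SAP 3.4.2, after Table A 39, and at the start of section 5. A reader might infer that the plan has no exposure adjustment anywhere. The documents support that only for what can be seen.
- **Unknown cut-off.** It is tempting to state a gap of 12-14 points as fact. That needs the untreated column to stop at Month 6, which is inferred, and an assumed 20% risk. If half the controls decline and their later time counts as untreated, the gap is about 6-8 points.
- **Listings.** One might infer that same-period figures could never be recovered. SAP 3.1 promises subject data listings for safety variables. If these carry dates, re-derivation may be possible; the visible text does not say.
- **Limited weight.** Unrelated events are those that neither investigator nor sponsor called related (SAP 1.5). With 37 controls, a 20% incidence has a 95% margin of about 1.96 × √(0.2 × 0.8/37) = ±13 points. That imprecision does not remove a bias that runs one way.
- **Related events.** The argument does not extend to Tables A 35-A 38. Injection reactions typically start on the day of treatment (Protocol 8.4.8), and the protocol already pooled related events.

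**Conclusion.** The concern holds as a minor point about the visible shells. Tables A 34 and A 39 set unrelated events side by side over unequal follow-up, as crude percentages, and no visible table gives a same-period comparison by randomised group.

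The direction follows from the visit schedule as long as the untreated column averages less time than the treated one, as it does in each scenario above. The size does not follow from the documents. It rests on an assumed background rate, a constant and equal hazard, control uptake, dropout, and a cut-off that the visible SAP leaves unstated.

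The serious sub-row under unrelated events has the same structure and shares the distortion. The any-AE and TEAE-total rows share it more weakly. Because the follow-up of controls who decline treatment is not assigned to a column, two analysts could produce different untreated percentages from the same data.

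**What to change.** 1. Add patient-years and events per patient-year to both columns of Tables A 34 and A 39.
2. State where the untreated column stops, and in which column events after Month 6 are counted for controls who decline treatment.
3. Restore the comparison of Protocol 10.5 as a summary by baseline group in the Safety population: all events by SOC and PT, and non-related events by SOC, PT and intensity. Count onsets over one fixed number of days from randomisation in both groups, ending before the control Month 6 injection. Days 1-175, cut at that injection if it comes earlier, is one workable choice. The Month 6 visit itself should not be the cut.
4. Keep the pooled treated data as a description of what happens after exposure.

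The cost is some SAP wording, extra cells in two shells, one or two more tables and a little programming. Event, randomisation and injection dates are already collected, so no new data are needed.

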3.5 Interim Analysis

Not applicable.

4 Determination of Sample Size

CCI

Effective

Effective date: 2017-04-21 09:20

 GALDERMA	<small>Title</small> Statistical Analysis Plan 43CH1507	<small>Doc id</small> MA-32268
--	---	--

CCI

5 Changes in the Analysis Planned in the Protocol

CCI

Cohorts used for analysis of adverse events will be defined differently, as follows.

Text in CSP:

“Since the no-treatment control group will receive treatment at the month 6 visit, only AEs occurring up until that time point will be included in this presentation, for both groups. Furthermore, all AEs will also be summarised by SOC and PT using the Perlane-L group for the whole study period, and also using the no-treatment group for the study period following their treatment at Month 6.”

Revised text in SAP:

“All AE summaries defined below will be presented by treatment (no treatment at baseline vs. all treated subjects).”

Version: 1.0

6 Reference List

 GALDERMA	Title Statistical Analysis Plan 43CH1507	Doc id MA-32268
---	--	----------------------------------

Table A 37. Time to onset (days) of related TEAEs, by MedDRA System Organ Class and Preferred Term (Safety).....	31
Table A 38. Action taken due to related TEAEs by MedDRA System Organ Class and Preferred Term (Safety).....	32
Table A 39. Unrelated TEAEs by MedDRA System Organ Class, Preferred Term and intensity (Safety).....	32

[figure not shown]

Table of figures

Figure A 1. Difference in MMVS responder rate (left and right midface combined) by site at Month 6, Blinded Evaluator (FAS)	16
---	----

[figure not shown]

Effective date: 2017-04-21 09:20

Effective

Version: 1.0

 GALDERMA	<small>Title</small> Statistical Analysis Plan 43CH1507	<small>Doc id</small> MA-32268
---	---	--

- Figure A 10. Proportion of subjects affected by a specific event (to any intensity level) after initial treatment (Safety) 35
- Figure A 11. Proportion of subjects affected by a specific event (to any intensity level) after touch-up (Safety) 35

 GALDERMA	Title Statistical Analysis Plan 43CH1507	Doc id MA-32268
---	---	--------------------

Table A 1. Subject disposition (all subjects)

Number of subjects		Perlane-Lido	Control	Total
Screened		-	-	xx
Screening failures				xx (%)
Randomized		xx	xx	xx
Completed primary endpoint		xx (%)	xx (%)	xx (%)
Completed		xx (%)	xx (%)	xx (%)
Withdrawn		xx (%)	xx (%)	xx (%)
Reason for withdrawal	Withdrawn consent	xx (%)	xx (%)	xx (%)
	Lost to follow-up	xx (%)	xx (%)	xx (%)
	Medical reason	xx (%)	xx (%)	xx (%)
	Other	xx (%)	xx (%)	xx (%)

% screening failures is based on total number of screened subjects.

% I/E criteria not met and withdrawn consent is based on the number of screening failures.

In all other cases: % is based on the number of randomized subjects.

Table A 2. Analysis populations (all randomized subjects)

Site	Subject Number	Safety		FAS		PP	
		n	%	n	%	n	%
Site 1	101-1xx	xx	xx.x	xx	xx.x	xx	xx.x
Site 2	201-2xx	xx	xx.x	xx	xx.x	xx	xx.x
Site x	x01-xxx	xx	xx.x	xx	xx.x	xx	xx.x
Total (N)	-	xx	100.0	xx	100.0	xx	100.0

% = n/N*100

 GALDERMA	Title Statistical Analysis Plan 43CH1507	Doc id MA-32268
---	--	----------------------------------

Table A 3. Subject accountability (all subjects in Perlane-Lido group)

Number of subjects	Observed	Missed	Withdrawals	Continuing on study
Baseline/initial treatment	xx	xx	xx	xx
4W follow-up/optional touch-up	xx	xx	xx	xx
4W follow-up	xx	xx	xx	xx
3M after last treatment	xx	xx	xx	xx
6M after last treatment	xx	xx	xx	xx
9M after last treatment	xx	xx	xx	xx
12M after last treatment	xx	xx	xx	xx

Table A 4. Subject accountability (all subjects in Control group)

Number of subjects	Observed	Missed	Withdrawals	Continuing on study
Baseline	xx	xx	xx	xx
4W follow-up	xx	xx	xx	xx
3M after baseline				
6M after baseline/treatment				
4W follow-up/optional touch-up				
4W follow-up				
3M after last treatment				
6M after last treatment				

 GALDERMA	Title Statistical Analysis Plan 43CH1507	Doc id MA-32268
---	---	--------------------

Table A 5. Withdrawn subjects

Site	Subject number	Group	Date of treatment		Last visit performed	Date of withdrawal	Reason for withdrawal
			Treatment	Optional touch-up			

Any extra comments here ...

Table A 6. Protocol deviations affecting PP population

Protocol deviation (category)	Number of subjects/Subject number	Number of deviations

(if only a few number of subjects, list subject numbers in second column)

Table A 7. Protocol deviation not affecting PP population

Protocol deviation category	Number of subjects	Number of deviations

 GALDERMA	Title Statistical Analysis Plan 43CH1507	Doc id MA-32268
---	---	----------------------------------

Table A 8. Demographic and baseline characteristics (FAS)

Variable	Parameter	Perlane-Lido N=XX	Control N=XX	Total N=XX
Age (years)	N	xx		
	Mean	xx.x		
	SD	xx.x		
	Median	xx.x		
	Minimum	xx.x		
	Maximum	xx.x		
Gender n (%)	Female	xx (xx.x)		
	Male	xx (xx.x)		
Baseline BMI	N	xx		
	Mean	xx.x		
	SD	xx.x		
	Median	xx.x		
	Minimum	xx.x		
	Maximum	xx.x		

% = n/N*100

Additional variables in this table:

- Ethnicity
- Baseline MMVS Blinded Evaluator, right and left side respectively
- CCI

 GALDERMA	Title Statistical Analysis Plan 43CH1507	Doc id MA-32268
---	---	----------------------------------

Table A 9. Subjects reporting medical history/concurrent disease and number of conditions by MedDRA System Organ Class (FAS)

Primary SOC	Perlane-Lido N=xx						Control N=xx					
	All			Ongoing at study start			All			Ongoing at study start		
	Events	Subjects	Events	Subjects	Events	Subjects	Events	Subjects	Events	Subjects	Events	Subjects
	n	n	%	n	n	%	n	n	%	n	n	%
	Xx	Xx	xx.x	Xx	Xx	xx.x	Xx	Xx	xx.x	Xx	Xx	xx.x
	Xx	Xx	xx.x	Xx	Xx	xx.x	Xx	Xx	xx.x	Xx	Xx	xx.x
Total1)	xx	xx	xx.x	Xx	xx	xx.x	xx	xx	xx.x	xx	Xx	xx.x

$\% = n / N * 100$

1) A single subject may have reported medical history (relevant or major illness) by more than one primary SOC category.

 GALDERMA	Title Statistical Analysis Plan 43CH1507	Doc id MA-32268
---	---	----------------------------------

Table A 10. Prior use of facial dermatological procedures (FAS)

Procedure	Perlane-Lido			Control		
	N=xx		Events	N=xx		Subjects
	Events	Subjects		Events	Subjects	
	n	n	%	n	n	%
Xxx	xx	xx	xx.x	xx	xx	xx.x
Xxx	xx	xx	xx.x	xx	xx	xx.x
Xx	xx	xx	xx.x	xx	xx	xx.x
	xx	xx	xx.x	xx	xx	xx.x
	xx	xx	xx.x	xx	xx	xx.x
	xx	xx	xx.x	xx	xx	xx.x
Total	xx	xx	xx.x	xx	xx	xx.x

% = n/N*100

 GALDERMA	Title Statistical Analysis Plan 43CH1507	Doc id MA-32268
---	---	----------------------------------

Table A 11. Subjects reporting concomitant medication (FAS)

Concomitant medication	Any concomitant medication?							
	Pelane-Lido N=xx				Control N=xx			
	No		Yes		No		Yes	
	n	%	n	%	n	%	n	%
Ongoing at study start								
Initiated during study								
Total								

% = n/N*100

Table A 12. Subjects reporting concomitant medication and number of medications by reason (FAS)

		Pelane-Lido N=xx		Control N=xx	
Reason for concomitant medication		No. of subjects	No. of drugs	No. of subjects	No. of drugs
Medical History	xx (xx.x)	xx	xx (xx.x)	xx	
Adverse Event	xx (xx.x)	xx	xx (xx.x)	xx	
Other	xx (xx.x)	xx	xx (xx.x)	xx	

% = n/N*100

 GALDERMA	Title Statistical Analysis Plan 43CH1507	Doc id MA-32268
---	---	----------------------------------

Table A 13. Subjects reporting concomitant medication and number of medications by ATC code (FAS)

ATC code	ATC text	Perlane-Lido N=xx			Control N=xx		
		Subjects		Medications	Subjects		Medications
		n	%	n	n	%	n
		Xx	xx.x	Xx	xx	xx.x	Xx
		Xx	xx.x	Xx	Xx	xx.x	Xx
		xx	xx.x	xx	Xx	xx.x	Xx

% = n/N*100

 GALDERMA	Title Statistical Analysis Plan 43CHI1507	Doc id MA-32268
---	--	----------------------------------

Table A 14. Concomitant medication taken due to an AE by ATC code (FAS)

Concomitant medication			Adverse Event	
ATC text (ATC code)	No of subjects	No. of drugs	MedDRA Preferred term	Related
ATC 1	Xx	Xx	PT 1	Yes/No
			PT 2	Yes/No
			-	Yes/No
ATC 2	Xx	Xx	PT	Yes/No
ATC 3	Xx	Xx	PT	Yes/No
-	Xx	Xx	-	Yes/No
Total	xx	xx	-	-

 GALDERMA	Title Statistical Analysis Plan 43CH1507	Doc id MA-32268
---	---	----------------------------------

Table A 15. Subjects reporting concomitant procedure/treatment by reason (FAS)

Reason for concomitant procedure/treatment	Pelane-Lido N=xx		Control N=xx	
	No. of subjects	No. of Procedures/ treatments	No. of subjects	No. of Procedures/ treatments
Medical History	xx (xx.x)	xx	xx (xx.x)	xx
Adverse Event	xx (xx.x)	xx	xx (xx.x)	xx
Other	xx (xx.x)	xx	xx (xx.x)	xx
Total	xx (xx.x)	xx	xx (xx.x)	xx

% = n/N*100

 GALDERMA	Title Statistical Analysis Plan 43CH1507	Doc id MA-32268
---	---	--------------------

Table A 16. MMVS responder rate by treatment and side of the face at Month 6, Blinded Evaluator (FAS)

Assessment/Time Point	Treatment Group	# of Subjects in FAS	# of Responders	Proportion of Responders	95% Confidence Interval	P-Value
Right and Left Midface Combined at Month 6	Perlane-Lido	Xx	Xx	X.XX	X.XX, X.XX	
	Control	Xx	Xx	X.XX	X.XX, X.XX	
	Difference	-	-	X.XX	X.XX, X.XX	X.XX
Right Midface at Month 6	Perlane-Lido	Xx	Xx	X.XX	X.XX, X.XX	
	Control	Xx	Xx	X.XX	X.XX, X.XX	
	Difference	-	-	X.XX	X.XX, X.XX	X.XX
Left Midface at Month 6	Perlane-Lido	Xx	Xx	X.XX	X.XX, X.XX	
	Control	Xx	Xx	X.XX	X.XX, X.XX	
	Difference	-	-	X.XX	X.XX, X.XX	X.XX

Note: Subjects with a missing MMVS have their values imputed using BOCF up to Month 6.

Note: Responder is defined as a subject with an improvement of at least one grade on the MMVS from baseline.

Note: Responder rate is calculated as the number of Responders at the visit of interest divided by the number of subjects in the FAS population for the specific treatment group.

Note: P-values for the difference in proportions are based on the Fisher's Exact test.

Note: 95% Confidence Intervals are two-sided confidence intervals calculated using the exact interval.

Table A 17. MMVS responder rate by treatment and side of the face at Month 6, Blinded Evaluator (PP)

As Table A 16 (only Left and Right Side Combined)

Note: No imputation is used for PP analysis. Only subjects with complete data are included.

Note: Responder is defined as a subject with an improvement of at least one grade on the MMVS from baseline.

Note: Responder rate is calculated as the number of Responders at the visit of interest divided by the number of subjects in the PP population for the specific treatment group.

CCI

 GALDERMA	Title Statistical Analysis Plan 43CH1507	Doc id MA-32268
--	---	----------------------------------

Table A 18. Sensitivity analysis for the MMVS responder rate by treatment and side of the face at Month 6, Blinded Evaluator (FAS)

As Table A 16 (only Left and Right Side Combined)

Note: Missing MMVS values are handled using multiple imputation methods.

Note: Responder is defined as a subject with an improvement of at least one grade on the MMVS from baseline.

Note: Responder rate is calculated as the number of Responders at the visit of interest divided by the number of subjects in the FAS population for the specific treatment group.

CCI

Table A 19. MMVS responder rate corrected for baseline MMVS by treatment and side of the face at Month 6, Blinded Evaluator (FAS)

As Table A 16 (only Left and Right Side Combined)

Note: Subjects with a missing MMVS have their values imputed using BOCF up to Month 6.

Note: Responder is defined as a subject with an improvement of at least one grade on the MMVS from baseline.

Note: Responder rate is calculated as the number of Responders at the visit of interest divided by the number of subjects in the FAS population for the specific treatment group.

CCI

 GALDERMA	<small>Title</small> Statistical Analysis Plan 43CHI1507	<small>Doc id</small> MA-32268
---	---	-----------------------------------

CCI

[figure not shown]
 GALDERMA	<small>Title</small> Statistical Analysis Plan 43CH1507	<small>Doc id</small> MA-32268
---	--	-----------------------------------

CCI

[figure not shown]
 GALDERMA	<small>Title</small> Statistical Analysis Plan 43CH1507	<small>Doc id</small> MA-32268
---	--	-----------------------------------

CCI

 GALDERMA	<small>Title</small> Statistical Analysis Plan 43CH1507	<small>Doc id</small> MA-32268
---	--	-----------------------------------

CCI

CCI

 GALDERMA	<small>Title</small> Statistical Analysis Plan 43CH1507	<small>Doc id</small> MA-32268
---	---	--

CCI

[figure not shown]

 GALDERMA	<small>Title</small> Statistical Analysis Plan 43CH1507	<small>Doc id</small> MA-32268
---	--	-----------------------------------

CCI

[figure not shown]
 GALDERMA	<small>Title</small> Statistical Analysis Plan 43CH1507	<small>Doc id</small> MA-32268
---	--	--

CCI

[figure not shown]
 GALDERMA	<small>Title</small> Statistical Analysis Plan 43CH1507	<small>Doc id</small> MA-32268
---	--	--

CCI

[figure not shown]
 GALDERMA	Title Statistical Analysis Plan 43CH1507	Doc id MA-32268
---	--	----------------------------------

CCI

[figure not shown]
 GALDERMA	<small>Title</small> Statistical Analysis Plan 43CH1507	<small>Doc id</small> MA-32268
---	--	-----------------------------------

CCI

 GALDERMA	<small>Title</small> Statistical Analysis Plan 43CHI1507	<small>Doc id</small> MA-32268
---	---	-----------------------------------

CCI

 GALDERMA	Title Statistical Analysis Plan 43CH1507	Doc id MA-32268
---	---	----------------------------------

Table A 32. Exposure to study treatment (Safety)

Assessment (Right and Left Midface Combined)		Perlane-Lido N=xx	Control (Optional Treatment) N=xx
Volume of injection (mL) for treatment	N	Xx	Xx
	Mean (SD)	x.xxx (x.xxx)	x.xxx (x.xxx)
	Median	x.xxx	x.xxx
	Min, Max	x.xx, x.xx	x.xx, x.xx
Volume of injection (mL) for touch-up	N	Xx	Xx
	Mean (SD)	x.xxx (x.xxx)	x.xxx (x.xxx)
	Median	x.xxx	x.xxx
	Min, Max	x.xx, x.xx	x.xx, x.xx
Total volume of injection (mL) for treatment+touch-up	N	Xx	Xx
	Mean (SD)	x.xxx (x.xxx)	x.xxx (x.xxx)
	Median	x.xxx	x.xxx
	Min, Max	x.xx, x.xx	x.xx, x.xx
Depth of injection for treatment	Subcutaneous	Xx (xx.x%)	Xx (xx.x%)
	Supraperiosteal	Xx (xx.x%)	Xx (xx.x%)
	Other	Xx (xx.x%)	Xx (xx.x%)
Depth of injection for touch-up	Subcutaneous	Xx (xx.x%)	Xx (xx.x%)
	Supraperiosteal	Xx (xx.x%)	Xx (xx.x%)
	Other	Xx (xx.x%)	Xx (xx.x%)
Method of injection for treatment	-	-	-
	-	-	-
	-	-	-
Method of injection for touch-up	-	-	-
	-	-	-

% = $100 * n/N$

 GALDERMA	Title Statistical Analysis Plan 43CH1507	Doc id MA-32268
---	---	----------------------------------

Table A 33. Treatment procedure (Safety)

Time Point	Assessment	Category	Perlane-Lido N=xx	Control (Optional Treatment) N=xx
Treatment	Local anaesthesia used?	Yes	Xx (xx.x%)	Xx (xx.x%)
		No	Xx (xx.x%)	Xx (xx.x%)
	Whereof topical cream		Xx (xx.x%)	Xx (xx.x%)
	Whereof local infiltration		Xx (xx.x%)	Xx (xx.x%)
Touch-up	Local anaesthesia used?	Yes	Xx (xx.x%)	Xx (xx.x%)
		No	Xx (xx.x%)	Xx (xx.x%)
	Whereof topical cream		Xx (xx.x%)	Xx (xx.x%)
	Whereof local infiltration		Xx (xx.x%)	Xx (xx.x%)
Treatment	Post-treatment care	None	Xx (xx.x%)	Xx (xx.x%)
		Massage	Xx (xx.x%)	Xx (xx.x%)
		Ice pack	Xx (xx.x%)	Xx (xx.x%)
		Other	Xx (xx.x%)	Xx (xx.x%)
Touch-up	Post-treatment care	None	Xx (xx.x%)	Xx (xx.x%)
		Massage	Xx (xx.x%)	Xx (xx.x%)
		Ice pack	Xx (xx.x%)	Xx (xx.x%)
		Other	Xx (xx.x%)	Xx (xx.x%)

% = $100 * n/N$

- Any device deficiencies will be listed in text or in a separate table, as appropriate.

	Title Statistical Analysis Plan 43CH1507	Doc id MA-32268
--	---	----------------------------------

Table A 34. Brief summary of all AEs (Safety)

	No treatment at baseline N=xx		Treatment with Perlane-Lido N=xx			
	Subjects		Event	Subjects		
	n	%	n	n	%	
Any AEs reported, total	xx	xx.x	xx	xx	xx.x	xx
Any TEAEs reported, total	xx	xx.x	xx	xx	xx.x	xx
Of which were serious	xx	xx.x	xx	xx	xx.x	xx
TEAEs related to product and/or injection procedure	xx	xx.x	xx	xx	xx.x	xx
Of which were serious	xx	xx.x	xx	xx	xx.x	xx
TEAEs unrelated to product and/or injection procedure	xx	xx.x	xx	xx	xx.x	xx
of which were serious	xx	xx.x	xx	xx	xx.x	xx
Subjects with no AE reported	xx	xx.x	-	xx	xx.x	-

Note: Treatment with Perlane-Lido columns include data from subjects in the Perlane-Lido group after their initial treatment at baseline, as well as data from subjects in the Control group after their initial treatment at Month 6.

% = $100 * n/N$

 GALDERMA	Title Statistical Analysis Plan 43CH1507	Doc id MA-32268
---	--	----------------------------------

Table A 35. Related TEAEs by MedDRA System Organ Class, Preferred Term, and intensity (Safety)

Primary System Organ Class Preferred Term	Intensity	No treatment at baseline N=xx		Treatment with Perlane-Lido N=xx	
		Events	Subjects	Events	Subjects
Any related AE	Total	Xx	Xx (xx.x)	Xx	Xx (xx.x)
	Mild	Xx	Xx (xx.x)	Xx	Xx (xx.x)
	Moderate	Xx	Xx (xx.x)	Xx	Xx (xx.x)
	Severe	xx	Xx (xx.x)	xx	Xx (xx.x)
SOC1	Total	Xx	Xx (xx.x)	Xx	Xx (xx.x)
	Mild	Xx	Xx (xx.x)	Xx	Xx (xx.x)
	Moderate				
	Severe				
PT11	Total				
	Mild				
	Moderate				
	Severe				
PT12	Total				
	Mild				
	Moderate				
	Severe				
SOC2	Total				
	Mild				
	Moderate				
	Severe				
PT21	Total				

Note: Treatment with Perlane-Lido columns include data from subjects in the Perlane-Lido group after their initial treatment at baseline, as well as data from subjects in the Control group after their initial treatment at Month 6.

% = $100 * n/N$

 GALDERMA	Title Statistical Analysis Plan 43CH1507	Doc id MA-32268
---	---	----------------------------------

Table A 36. Duration (days) of related TEAEs by MedDRA System Organ Class and Preferred Term (Safety)

	No treatment at baseline N=xx							Treatment with Perlane-Lido N=xx						
	Ongoing	n	Mean	SD	Min	Median	Max	Ongoing	n	Mean	SD	Min	Median	Max
General disorders and administration site conditions														
Injection site xxx														
Injection site xxx														
ALL														

Note: Treatment with Perlane-Lido columns include data from subjects in the Perlane-Lido group after their initial treatment at baseline, as well as data from subjects in the Control group after their initial treatment at Month 6.

% = 100*n/N

Table A 37. Time to onset (days) of related TEAEs, by MedDRA System Organ Class and Preferred Term (Safety)

	No treatment at baseline N=xx							Treatment with Perlane-Lido N=xx						
	n	Mean	SD	Min	Median	Max	n	Mean	SD	Min	Median	Max		
General disorders and administration site conditions														
Injection site xxx														
Injection site xxx														
ALL														

Note: Treatment with Perlane-Lido columns include data from subjects in the Perlane-Lido group after their initial treatment at baseline, as well as data from subjects in the Control group after their initial treatment at Month 6.

% = 100*n/N

 GALDERMA	Title Statistical Analysis Plan 43CH1507	Doc id MA-32268
---	---	----------------------------------

Table A 38. Action taken due to related TEAEs by MedDRA System Organ Class and Preferred Term (Safety)

[figure not shown]
System Organ Class Preferred Term	Action Taken							
	No treatment at baseline N=xx				Treatment with Perlane-Lido N=xx			
	None	Medication treatment	Non-pharmacological treatment or other procedures/tests	Subject withdrawn	None	Medication treatment	Non-pharmacological treatment or other procedures/tests	Subject withdrawn
General disorders and administration site conditions								
Injection site xxx								
Injection site xxx								
SOC 2								
PT 1								
PT 2								
...								
All								

Table A 39. Unrelated TEAEs by MedDRA System Organ Class, Preferred Term and intensity (Safety)

As Table A 35

[figure not shown]
 GALDERMA	<small>Title</small> Statistical Analysis Plan 43CHI1507	<small>Doc id</small> MA-32268
---	---	--

CCI

 GALDERMA	<small>Title</small> Statistical Analysis Plan 43CH1507	<small>Doc id</small> MA-32268
---	--	--

CCI

 GALDERMA	<small>Title</small> Statistical Analysis Plan 43CH1507	<small>Doc id</small> MA-32268
---	--	-----------------------------------

CCI

[figure not shown]

Figure A 11. Proportion of subjects affected by a specific event (to any intensity level) after touch-up (Safety)

As Figure A 10

 GALDERMA	Title Statistical Analysis Plan 43CH1507	Doc id MA-32268
--	---	----------------------------------

2017-04-21 09:20

Effective date:

Effective

Version: 1.0

SIGNATURES PAGE

Date	Signed by
2017-04-20 15:12	PPD
Justification	Approved by Owner
2017-04-21 06:29	PPD
Justification	Approved by Technical Expert
2017-04-21 07:58	PPD
Justification	Approved by Project Manager
2017-04-21 08:38	PPD
Justification	Approved by Technical Expert
2017-04-21 09:20	PPD
Justification	Approved by Technical Expert
